Study number: EUP/HED/008/2016 VERSION DATE: 21.11.2016

ASSESSMENT OF THE EFFICACY OF THE HEDUSSIN® MEDICINAL PRODUCT USE IN THE TREATMENT OF PRODUCTIVE (WET) COUGH

PROTOCOL FOR A NON-INTERVENTIONAL STUDY

STUDY NUMBER: EUP/HED/008/2016

MEDICINAL PRODUCT NAME: HEDUSSIN®

Name of the Marketing Authorisation Holder:

Phytopharm Klęka S.A. [name] Contact in case of adverse effects:

[contact]

Person responsible for the pharmacotherapy

safety on behalf of the Sponsor: [name], [contact]

[name]: [name]

Office of the Study Organizer:

Europharma M. Rachtan Sp. z o.o. [name]

[contact] [contact]

Name of the Coordinator:

prof. [name] [name], associate professor

LEGAL NOTICE

This Protocol does not in any way constitute a basis for a decision on any diagnostic or therapeutic methods with respect to any participant of the Study.

Europharma M. Rachtan Sp. z o.o. acts as the organizer of the study (CRO - Contract Research Organizer) as requested by the Marketing Authorization Holder: **Phytopharm Klęka S.A**.

DOCUMENT STATUS: CONFIDENTIAL

SIGNATURES UNDER THE PROTOCOL

Investigator Signature:

I confirm that I have read the Protocol for the non-interventional observational study entitled:

ASSESSMENT OF THE EFFICACY OF THE MEDICINAL PRODUCT HEDUSSIN® IN THE TREATMENT OF PRODUCTIVE (WET) COUGH

I am aware of the investigator's responsibilities imposed on me resulting from binding regulations and the Study Protocol. I agree to conduct this study in accordance with these guidelines.

Name and last name	Signature
Position: Investigator	
Address of the Medical Centre:	Date:

DOCUMENT STATUS: CONFIDENTIAL

PROTOCOL SUMMARY

PROJECT TITLE	ASSESSMENT OF THE EFFICACY OF THE HEDUSSIN® MEDICINAL PRODUCT USE IN THE TREATMENT OF PRODUCTIVE (WET) COUGH	
THE AIMS:	Main aim of the Study: The assessment of the efficacy of the HEDUSSIN® medicinal product use in the treatment of productive (wet) cough evaluated on the basis of the severity and the treatment time of the infection occurring with a productive (wet) cough of various aetiologies in children aged 2-12. Additional aim of the Study: The assessment of the treatment tolerance.	
PHASE OF THE	Non-interventional, multicentre, open-label, post-authorization study.	
STUDY:	Observational Study of the efficacy of the treatment (PAES – Post Authorization Efficiency Study)	
DESIGN OF THE STUDY:	The staff that will take part in the study consists of paediatricians, general practitioners, internists, allergists, pulmonologists or doctors currently in the process of obtaining these specializations who lead the treatment of patients (in the form of outpatient healthcare) suffering from productive cough of various aetiologies in which, due to clinical indications, the HEDUSSIN® medicinal product has been introduced. Data on the efficacy of the treatment with the HEDUSSIN® medicinal product will be gathered in the Study Questionnaires (SQ) during two subsequent routine visits: first (1), where the Patient will be included in the Study, and second (2) approximately 7-10 days after the first one. The visits will be scheduled in accordance with the needs resulting from the Patient's clinical state. The inclusion of the Patient into the group where the given treatment method is used should not result from the Study Protocol. It should be dependent solely on the current medical practice and remain in accordance with the current medical knowledge. The medical history collection period, conducted by 50 investigators, is scheduled for 3 months.	
STUDY POPULATION	Patients (N=500) aged 2-12 of both sexes, diagnosed with productive (wet) cough of various aetiologies.	
MEDICINAL PRODUCT TO BE USED IN THE STUDY	In 100ml of the syrup, HEDUSSIN ® contains 825g of dry extract of ivy leaves. It is a medicine in the form of a brown, opalescent liquid of sweet flavour, possibly with a light sediment. HEDUSSIN ® is recommended productive (wet) cough of various aetiologies as an expectorant.	
ENDPOINTS:	Endpoints and methods of their assessment:	
	The gathering of information on the therapeutic effects of the treatment with the HEDUSSIN® medicinal product based on the evaluation of the severity of the symptoms associated with the respiratory system, the Patient's overall wellbeing and the duration of the infection. All adverse effects caused by the drug must be reported to Phytopharm Klęka S.A. and to the URPL. Additionally, they can be reported to the Study Organizer via the website:	
AT 4 TIQT: 2	www.dzialanianiepozadane.com	
STATISTICAL METHODS:	The sample size of 500 Patients was based on the feasibility study. The analysis of the data obtained in the Study will be descriptive: the compiled data will consist of summarizing statistics such as quantities, average values, standard deviations, medians, minimal and maximal values of the observed frequencies/proportions. The effectiveness analysis will be conducted on the basis of the population of Patients who will partake in all of the visits described in the Study Protocol.	

Table of contents

Study number: EUP/HED/008/2016 VERSION DATE: 21.11.2016

1. INT	RODUCTION	6
1.1.	Basic information on the subject affliction of this Study	6
1.2.	Information on the study drug	7
1.3.	The clinical reason for conducting this Observational Study	8
2. TH	E AIM OF THE STUDY	9
2.1.	The main aim of the Study	9
2.2.	The additional aim of the Study	9
3. STU	JDY DESIGN	10
3.1.	Basic information	10
3.1.	1. Characteristics of the study population	10
3.1.2	2. Study design	10
3.2.	Endpoints	10
3.3.	Substantiation of the study construction	10
3.4.	Duration of the Study	11
4. CO	MPLIANCE WITH TERMS OF GOOD CLINICAL PRACTICE, ETHICAL ISSUES.	11
5. STU	JDY POPULATION	11
5.1.	Records of the Study participants	11
5.2.	Inclusion criteria	12
5.3.	Exclusion criteria	12
5.4.	Procedures for treatment discontinuation or if the patient withdraws from the study	12
6. ME	THODOLOGY	12
6.1.	Schedule of the Study	12
6.2.	Assessments in a specialist and primary care clinics under the study	13
6.2.	1. Initial visit (Visit 1) - (day 0)	13
6.2.2		•
	the clinical needs of the Patient	
	SESSMENTS PERFORMED IN THE STUDY	
7.1.	Endpoints and the methods of their evaluation	
7.1. ⁻		
	JDY DRUG	
8.1.	Administration of the drug	
8.2.	Patient identification	
8.3.	Drug delivery	
8.4. 9. REI	Concomitant medication PORTING RELATED ADVERSE EFFECTS	
	TATISTICAL CONSIDERATIONS	
10. 5		
IU.I.	F QUEIL GIQSSIIIGAUUT ATU UEIITIUUT	10

DOCUMENT

STATUS: CONFIDENTIAL

10.2	2.	Analyses, populations, definitions	16
10.3	3.	Method of determining the sample size	17
10.4	1.	Statistical analysis	17
1	0.4.1	. Demographic data and other basic characteristics	17
1	0.4.2	2. Distribution of patients and cases of exclusion from the study	17
1	0.4.3	3. Adverse effects analysis	17
10.5	5.	Factors which may affect the statistical analysis and modify the results of the Study	18
10.6	6.	Factors limiting the Study	18
11.	M	ONITORING PROCEDURES	18
12.	MA	ANAGEMENT OF THE STUDY	18

1. INTRODUCTION

Study number: EUP/HED/008/2016

VERSION DATE: 21.11.2016

1.1. Basic information on the subject affliction of this Study

Cough is a reflex defence reaction in response to factors irritating the nerve endings present in the mucous membrane of the upper respiratory passages. The coughing reflex results in a sudden contraction of both the chest muscles and the diaphragm initially occurring with the closure of the glottis which, in turn, results in a rapid expulsion of air from the respiratory passages at the moment of its opening.

The coughing reflex can be triggered by damaging the mucous membrane of the upper respiratory passages in course of viral and bacterial infections, by a foreign matter in the respiratory passages themselves or through the irritation of the nerves responsible for the conduction of this reflex's impulses. e.g. through the irritation of the auricular branch of the vagus nerve.

Cough is characterised as a wet (productive) one if it is accompanied by secretion expectoration (either mucous or purulent). In the children population, it is often swallowed. Cough is described as a dry one if it is not accompanied by the abovementioned expectoration of secretion. Dry cough often appears in the initial phases of (often viral) infections and later evolves into a productive cough.

An etiological factor which is definitively more rare in the population of children are primary infections of the respiratory passages. However, bacteria can be a cause of viral respiratory tract superinfections. In the population of children, productive cough is often caused by the inflammation of the upper sections of the said tract but also by (most commonly) chronic rhinitis or by sinusitis (ethmoidal sinus inflammation in younger children; the other sinuses develop fully after the age of 6). This type of cough is defined as one related to upper airways.

The cough which is characteristic for viral infections of the upper respiratory passages, due to the damage made to the mucous membrane of the upper airways and the irritation of the nerve endings present there, may last up to 4 weeks and it is then characterised as acute.

Common causes of chronic cough in the children population include bronchial asthma. The symptom of which may be bronchitis occurring with an obturation. Allergic rhinitis can also be a common cause. Less common causes of chronic cough in children include inherited diseases, cystic fibrosis or syndromes associated with the disturbance of the activity of the airways' mucous membrane cilia. They are characterised by an early symptom onset, a more severe clinical course and disorders of many internal organs. In case of chronic cough in children, it is advised to always undergo an appropriate diagnostic which takes into account the possibility of the aspiration of a foreign body into the bronchial tree as well as causes of cough which are not associated with the respiratory system, e.g. gastroesophageal reflux or psychogenic causes.

Productive cough is a form of the bronchial tree's cleansing procedure as it allows the evacuation of the secretion retained in it. Therefore, it should not be inhibited pharmacologically. Instead, medicine that dilutes the secretion and facilitates its expectoration should be used.

Substances used in the treatment of wet cough demonstrates the following activity:

- Expectorant; secretolytic activity which increases the volume of the secretion and enhances improves its parameters,
- Mucolytic which reduce the secretion viscosity,
- Mucokinetic, which increase the effectiveness of the ciliary transport

One of the expectorants which increase the volume of the secretion is an herbal medicine obtained from common ivy leaves. The ivy extract contains triterpenoid saponins (hederacoside B & C) which grant it the secretolytic and antioxidant properties. They stimulate the coughing reflex and increase the secretion production on the basis of a reflex from the vagus nerve, through the irritation of the nerve endings in the mucous membrane of the stomach. Moreover, the ivy leaves extract demonstrates spasmolytic activity in relation to the smooth muscles of the bronchial walls which additionally facilitates the evacuation of the secretion [2].

The secretolytic, mucolytic and spasmolytic activity mechanism of the ivy leaves was proved on the basis of the fluorescence correlation spectroscopy microscopic method.

 α -hederin, formed from the hederacoside C contained in the extract, increases the production of the surfactant in the lung alveoli ^[9] through the stimulation of the β_2 -adrenergic receptors. The stimulation of the β_2 -adrenergic receptors also results in the relaxation of the airways' smooth muscles by decreasing their elastic resistance. Moreover, it improves the mucociliary clearance of the bronchi ^[10].

The conducted clinical research also indicated the potential anti-inflammatory and antifungal activity of the common ivy leave extract.

It is recommended that the treatment with the preparations including the ivy leave extract lasts approximately 7 days [3]. The preparation should not be used in the evening. Caution is recommended when administering the preparation in Patients suffering from gastritis and peptic ulcer disease.

The effectiveness of the ivy leave extract use in the children population (aged 2-10) with symptoms of acute bronchitis was comparable to acetylcysteine. Furthermore, it depicted demonstrated better tolerance [4].

The clinical research on the efficacy of the common ivy leave extract was conducted also in the adult population suffering from both acute and chronic diseases of the respiratory system (lung obstructive diseases, chronic bronchitis) [5, 6, 7, 8].

1.2. Information on the study drug

HEDUSSIN® (active substance: dry ivy leave extract).

HEDUSSIN[®] is recommended for use in treatment of wet cough of various aetiology as an agent facilitating expectoration – expectorant – in both adults and children. The medicine is administered orally and should be shaken before use.

In children aged 2-5, it is recommended to administer 2 ml of the syrup twice daily (which corresponds to 33 mg of dry ivy leave extract daily).

In children aged 6-12, it is recommended to administer 4 ml of the syrup twice daily (which corresponds to 66 mg of dry ivy leave extract daily).

In adults and children above the age of 12, it is recommended to administer 6 ml of the syrup twice daily (which corresponds to 99 mg of dry ivy leave extract daily).

Contraindications for the use of the dry extract of ivy leaves include:

- Hypersensitivity to the active substance, other plants from the Araliaceae family or any of the
 excipients (non-crystallizing liquid sorbitol, potassium sorbate, xanthan gum, anhydrous citric
 acid)
- Age below 2 years.

Persistent or recurring cough in children aged 2 to 4 requires a thorough diagnostic before the commencement of the treatment.

In case of the occurrence of dyspnoea, fever or purulent sputum, one should seek advice from a doctor or pharmacist.

It is not recommended to administer the **HEDUSSIN**^R syrup concomitantly with antitussive medicine such as codeine or dextromethorphan. Caution is recommended when administering the syrup in Patients suffering from gastritis or the peptic ulcer disease.

The HEDUSSIN® syrup contains sorbitol, therefore it should not be used by Patients with rare inherited fructose intolerance disorders.

There is no data on the influence of the medicinal product on fertility. The usage safety during pregnancy and breastfeeding has not been established. Therefore, it is not recommended to use the product during that time.

The research on the influence of the preparation on the ability to operate machines has not been conducted.

Interactions with other medicinal products and other forms of interactions

No research conducted.

Study number: EUP/HED/008/2016

VERSION DATE: 21.11.2016

Adverse effects resulting from the use of the HEDUSSIN® medicinal product include:

- Very common (≥ 1/10): none
- Common (≥1/100 to <1/10): nausea, vomiting, diarrhoea
- Uncommon (≥1/1000 to <1/100): allergic reactions (hives, skin rash, angioedema, dyspnoea)
- Rare (≥1/10 000 to <1/1000): none
- Very rare (<1/10000): none
- Frequency not known: none

Overdosage

Administering a dose exceeding the recommended one may cause nausea, vomiting, diarrhoea and agitation. The treatment is symptomatic. Individual cases of overdosage were reported in children aged 4. Accidental administration of a large dose of the ivy extract (correspondent to 1,8 g of ivy leaves approximately equal to 36 ml of the **HEDUSSIN®** syrup) resulted in agitation and diarrhoea.

1.3. The clinical reason for conducting this Observational Study

HEDUSSIN[®] is a preparation containing dry extract of common ivy leaves as the active substance (825mg in 100 ml of the syrup) which is recommended in the treatment of wet cough of various aetiologies.

HEDUSSIN®, a medicinal product containing dry extract of common ivy leaves in the form of syrup, obtained the marketing authorisation (no. 22652) for medicinal products in Poland on 20.08.2015. Therefore the Study focusing on the assessment of the efficacy of the treatment in patients diagnosed with productive cough of various aetiologies is especially important to obtain data from the Polish population (the hitherto effectiveness findings were not obtained from the research on the Polish population). The data will be used for the purposes of planned marketing campaigns as well as staff, doctor and pharmacist trainings. The planned study of the HEDUSSIN® medicinal product can be carried out only on the trade name, as the subject of research interest is the specific medicinal product, administered in the form of syrup.

2. THE AIM OF THE STUDY

2.1. The main aim of the Study

The assessment of the efficacy of the **HEDUSSIN**® medicinal product use in the treatment of productive (wet) cough evaluated on the basis of the severity and the treatment time of the infection occurring with a productive (wet) cough of various aetiologies in children aged 2-12.

The assessment of the efficacy of the **HEDUSSIN®** medicinal product will be based on:

- 1. Observation of the below symptoms and changes in their intensity during the treatment*:
 - The severity of the cough (from 0 to 4)
 - Dyspnoea (from 0 to 4)
 - Auscultatory changes (wheezing, dry rale, crackles) (from 0 to 4)
 - Chest pain during cough (from 0 to 4)
 - Hoarse breathing (from 0 to 4)

0- absent; 1- mild; 2- moderate; 3- severe; 4- very severe

- 2. Determination of the infection duration (measured in days)
- 3. Evaluation of the body temperature
- 4. The use of concomitant treatment:
 - The inclusion of an antibiotic
 - The inclusion of other medications and dietary supplements

2.2. The additional aim of the Study

The assessment of the tolerance of the recommended therapy in the course of the infection with wet cough.

The assessment of the tolerance of the **HEDUSSIN®** syrup has been conducted on the basis of:

- 1. Sleep quality disturbances (intermittent sleep, shallow sleep, insomnia)
- 2. The feeling of weakness*

*The evaluation will be conducted on the basis of a 5-level estimation scale where:

0- absent; 1- mild; 2- moderate; 3- severe; 4- very severe

3. The VAS scale focused on the overall wellbeing (from 0 to 10)

^{*}The assessment will be carried out on the basis of the BSS (Bronchitis Severity Score) scale where:

3. STUDY DESIGN

3.1. Basic information

Study number: EUP/HED/008/2016

VERSION DATE: 21.11.2016

This is a post-authorization study. Data on the efficacy of the **HEDUSSIN®** medicinal product in the treatment of Patients diagnosed with productive (wet) cough of varying aetiology.

The medicinal product will be used in the usual manner strictly in accordance with the terms of the marketing authorization and in the manner specified in the Summary of Product Characteristics.

Patient inclusion into the study is independent from the previous decision regarding the treatment with **HEDUSSIN**®.

3.1.1. Characteristics of the study population

The study population will consist of patients aged 2 to 12 of both genders, diagnosed with wet cough of various aetiologies.

3.1.2. Study design

This project is an open-label, non-randomized, multicentre, non-interventional, post-authorization efficacy study (PAES).

3.2. Endpoints

The gathering of information on the therapeutic effects of the treatment with the **HEDUSSIN®** medicinal product includes the assessment of: the number of days until full recovery of the Patient measured from the day of the 1st visit until the closure of the observation – the day of the 2nd visit.

- Exclusion from the Study the number of days measured from the day of the 1st visit until the occurrence of complications, intensification of the state, occurrence of additional infections, etc.

 visit 2: closure of the observation and the conducting of a medical interview on the health status/Patient wellbeing.
- The change in the intensity of the symptoms, associated with the respiratory system, resulting
 from the treatment will be assessed on the basis of the BSS scale (Bronchitis Severity Scale)
 (evaluation of the measurements taken during visit 1 and 2)
- The evaluation of the changes in the overall wellbeing resulting from the treatment will be based on the VAS scale (Visual Analog Scale) (evaluation of the measurements taken during visit 1 and 2)
- The evaluation of the treatment tolerance based on the occurrence of sleep quality disturbances and weakness feeling will take place on the basis of a 5-level estimation scale (evaluation of the measurements taken during visit 1 and 2)

All adverse effects caused by the drug must be reported to **Phytopharm Klęka S.A.** or the URPL or to the Study Organizer via the **www.dzialanianiepozadane.com** website.

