3.4. Duration of the Study

The Observation of the Patients during the Study will continue up to 10 days from the date of the first visit. The number of assessments will not influence neither the number of visits nor the amendment of the therapy application as specified in the SPCh criteria. The duration of the study is 3 months.

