6. METHODOLOGY

6.1. Schedule of the Study

A summary of observations and assessments that will be conducted during the study is presented in the following table.

Table1. Schedule of the assessments during the Study realisation

PROTOCOL FOR A NON-

INTERVENTIONAL

STUDY

Procedures for particular assessments	Visit 1*	Visit 2*
Demographic data	Х	
Qualification of the Patient into the PAES Study (inclusion criteria)	Х	
History concerning comorbidities and their treatments	Х	Х
Basic diagnosis and its duration	Х	
The dose of the medicinal product used		Х
The assessment of :		
 The symptoms associated with the respiratory system (BSS scale) 		
Assessment of the body temperature	Χ	Х
Assessment of the overall wellbeing (VAS scale)		
Assessment of the sleep quality disturbances		
The use of concomitant treatment		
Duration of the infection (number of days)		Х
Reporting adverse effects related to the HEDUSSIN ® medicinal product use		Х

^{*}The assessments will take place as part of the routine Patient observation

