6.2. Assessments in a specialist and primary care clinics under the study

6.2.1. Initial visit (Visit 1) - (day 0)

The Study Questionnaire of Patients using the **HEDUSSIN®** medicinal product, in accordance with the leading physician as well as in accordance with the marketing authorization criteria, shall contain the following information:

- patient number;
- patient initials;
- demographic data;
- interview data on comorbidities;
- initial diagnosis;
- data on the long-term medicine administration in the treatment of comorbidities;
- decision on the Patient's compliance with the inclusion criteria and noncompliance with the exclusion criteria;
- data on the recommended dose of the HEDUSSIN® medicinal product;
- the assessment of the following symptoms:
 - 1. cough severity (from 0 to 4)
 - 2. dyspnoea (from 0 to 4)
 - 3. auscultatory changes during the cough (from 0 to 4)
 - 4. chest pain during the cough (from 0 to 4)
 - 5. hoarse breathing (from 0 to 4)
 - *in accordance with the 5-level BSS scale (Bronchitis Severity Scale) where:
 - 0- absent; 1- mild; 2- moderate; 3- severe; 4- very severe

Study number: EUP/HED/008/2016

VERSION DATE: 21.11.2016

- assessment of the body temperature;
- evaluation of the weakness feeling* *on a 5-level estimation scale where: 0- absent; 1- mild; 2- moderate; 3- severe; 4- very severe
- assessment of the overall wellbeing using the VAS scale;
- assessment of the sleep quality disturbances;
- the used concomitant treatment.
- 6.2.2. Visit 2 (approximately 7-10 days after the previous visit) in accordance to the schedule resulting from the clinical needs of the Patient

The Patients will be present on the control visits in the study centre at the scheduled time. During these visits, the Investigator will collect and record in the Study Questionnaire (SQ) the following information:

Duration of the infection (number of days until the symptoms receded)

A secondary conducting of:

- The assessment of the symptoms associated with the respiratory system on the basis of the BSS scale
- The evaluation of the body temperature
- The assessment of the weakness feeling on the basis of a 5-level estimation scale
- The assessment of the wellbeing based on the VAS scale
- The assessment of the sleep quality disturbances
- The used concomitant treatment

The Patient Observation last approximately 10 days.

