7.1. Endpoints and the methods of their evaluation

7.1.1. Assessment of the efficacy of the treatment

> Data on the current clinical status of the Patient will be collected during the 2 visits scheduled in the Study Protocol. The efficacy will be assessed on the basis of the assessment of the intensity of the symptoms associated with the respiratory system, the overall wellbeing of the Patient, the duration of the infection and the duration of the WET cough on the day of the first and second assessment.

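### The duration endpoint ends at full recovery in section 3.2 but at receding of symptoms in the Visit 2 data item, and neither event is defined

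*Protocol*

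**What the plan says.** The duration outcome appears in several places in the protocol:

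- **Section 2.1, main aim:** efficacy is "evaluated on the basis of the severity and the treatment time of the infection". The list of measures in the same section then names "Determination of the infection duration (measured in days", with no start or end.
- **Section 3.2, endpoints:** "the number of days until full recovery of the Patient measured from the day of the 1st visit". This is the only place that gives a start day.
- **Section 6.1, Table 1:** one row, marked at Visit 2 only: "Duration of the infection (number of days". There is no definition.
- **Section 6.2.2, Visit 2:** among the items the investigator enters in the Study Questionnaire: "Duration of the infection (number of days until the symptoms receded". This is the only passage that says how the collected item ends.
- **Section 7.1.1:** efficacy also rests on "the duration of the infection and the duration of the WET cough on the day of the first and second assessment", which adds a wet-cough duration without defining either.
- **Section 10.2:** infection duration is one of the three efficacy outcomes analysed.

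Five respiratory items (cough, dyspnoea, auscultatory changes, chest pain on coughing, hoarse breathing) are each scored from 0, absent, to 4, very severe, at Visit 1 and Visit 2 (sections 2.1, 3.2 and 6.2). On follow-up, section 3.4 says: "The Observation of the Patients during the Study will continue up to 10 days from the date of the first visit".

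**The concern.** The endpoint and the item that supplies it use different words for the event that stops the count. Full recovery is a demanding event. Receding can mean that symptoms have gone or that they have eased. The protocol does not say which symptoms must have changed, or how far. Section 5.1 plans for 50 physicians, each of whom would have to decide. Section 12.3 plans no source data verification that might expose different habits.

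Infection duration belongs to the main aim, and sections 1.3 and 3.3 say the data will be used in marketing campaigns and training. In an open-label, non-randomised study with a largely descriptive analysis, a reported number of days means only what its end event means. If some or all entries reflect easing rather than resolution, the study reports a faster recovery than section 3.2 defines, and physicians' results can differ through wording alone.

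**Working it through.** The protocol has no figure to reproduce here, so the check compares passages and then asks what the difference could do to the number of days.

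**1. Does any passage reconcile the two wordings?** No. Sections 2.1, 6.1 and 10.2 name a duration without an end event. Section 7.1.1 refers to the two assessment days and adds a second duration. Nothing defines full recovery or receded, or links either to a score.

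**2. Can the two events differ for one child?** Take a cough scored 3 at Visit 1 and 1 at Visit 2, with the other four items at 0.

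| Reading of the Visit 2 item | Entry for this child |
|---|---|
| Symptoms gone | No recovery day; not recovered by Visit 2 |
| Symptoms lessened | A day count before or at Visit 2 |
| Full recovery, as in section 3.2 | No recovery day; not recovered by Visit 2 |

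The first and third rows agree. The second does not, and it gives a recovery day to a child whose own Visit 2 cough score is above 0.

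**3. Could the analysis recover the right day later?** No. The scores exist only for Visits 1 and 2, so they show whether a child was symptom-free at Visit 2 but not on which day that began. The recorded day is the sole source.

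**4. Direction and size.** Let D be the days to complete resolution and f the fraction of D at which symptoms are judged to have receded, with f at most 1. The recorded duration is f × D, and the shortening is (1 − f) × D.

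The documents give neither D nor f. Purely as an assumption, take D = 8 days:

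| f | Recorded, f × 8 | Shortening, (1 − f) × 8 |
|---|---|---|
| 1 (receded means gone) | 8.0 | 0 |
| 0.9 | 7.2 | 0.8 |
| 0.8 | 6.4 | 1.6 |
| 0.6 | 4.8 | 3.2 |

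The sign is fixed: the shortening is never negative, and it is zero only at f = 1. The size is wholly determined by the assumed f, so the table shows how the result depends on f and is not an estimate.

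**The case against.** **The two wordings may mean the same.** The section 6.2.2 item is headed as the duration of the infection, and an infection lasts until it is over. On that reading receded means gone, and nothing is lost. This is a natural reading and no passage excludes it. It stands as far as this: the documents show that entries may differ, not that they will. It does not remove the need to say which reading applies.

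**A reader might infer a third end event from the main aim**, namely the end of treatment. The documents do not support that. The phrase in section 2.1 names a period, the same section restates it as infection duration, and nothing says the count stops when the syrup stops. It is loose wording only.

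**A reader might infer a bias of several days.** That would rest on a chosen value of f, and the honest range starts at 0.

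**The questionnaire is not shown.** Whether physicians see the word receded on the form is unknown; Table 1 omits it. This limits the claim to the protocol's description of the form.

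**Data checking exists.** Sections 11 and 12.4 send inconsistent entries back to the investigator. A recovery day beside a positive Visit 2 score could be queried, but this check is not named, and without a definition the entry is not clearly inconsistent.

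**The consequence is bounded.** No hypothesis, threshold or sample-size calculation rests on duration, and the change in symptom scores is a separate measure that is unaffected. This stands.

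**Conclusion.** The concern holds between sections 3.2 and 6.2.2. The stated endpoint ends at full recovery, while the collected item ends when symptoms receded. Both are undefined and neither is linked to the recorded scores. One variable may therefore mix partial improvement with complete resolution, and a recovery day may sit beside a Visit 2 score above 0.

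The effect on the reported duration is nil if every physician reads receded as gone, and downward to the extent that some read it as lessened. The documents do not allow the size to be estimated.

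The conclusion assumes that the questionnaire follows section 6.2.2. It deserves correction before questionnaires are issued, since a main efficacy outcome depends on an entry that cannot be rebuilt afterwards.

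**What to change.** 1. Use one end event, complete resolution, in sections 3.2 and 6.2.2 and in the Study Questionnaire.
2. Word the Visit 2 item as the day, by parent report and counted from Visit 1, on which the last of the cough and the other symptoms a parent can observe had gone. The first day with all five items at 0 would not work as the recorded event: auscultatory changes are scored only at the visits, and sections 3.3 and 11 rule out additional monitoring.
3. Accept that day only if all five respiratory items are 0 at Visit 2. Otherwise classify the child as not recovered by Visit 2, with no recovery day.
4. Report the proportion recovered by Visit 2 alongside the duration, because the durations then describe recovered children only.
5. In the main aim, replace treatment time with duration of the infection, for consistency.

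The cost is one reworded item, a few aligned sentences and one data check that fits the query process in sections 11 and 12.4. No visit or procedure is added. The reported duration will be somewhat longer and fewer children will count as recovered. The day remains a parent's recollection. The rule defines recovery by respiratory symptoms, so the sponsor should say so if temperature or weakness is also meant to count.
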